## 5 STATISTICAL METHODOLOGY AND STATISTICAL ANALYSES

### 5.1 Statistical Hypotheses

The primary hypothesis is

$$H_0 : S_1(t) = S_2(t) \text{ (all } t \text{)}$$

$$H_A : S_1(t) \neq S_2(t) \text{ (at least some } t \text{)}$$

where  $S_1(t)$  and  $S_2(t)$  are the survival functions of each compared treatment, respectively. For the primary endpoint TCPR [REDACTED], survival functions will be compared between Test NPX and [REDACTED], between Test NPX and [REDACTED] Tablet, and between each naproxen product and placebo.

### 5.2 Statistical Decision Rules

To control the family-wise Type I error rate at 0.05 for primary and secondary endpoints, the fixed sequence testing with fallback method will be used [Wiens 2003]. [Table 2](#) presents the order of the tests and the assigned  $\alpha$  values for each ordered test. Testing will commence with an assigned alpha = 0.049 and an alpha value of 0.001 will be reserved for the comparison of Test NPX and placebo on the percentage of subjects with confirmed perceptible relief from 45 minutes to successively earlier minutes in one-minute increments.

**Table 2: Order of Tests and Assigned Alpha Values**

---

	Pre-Assigned <math>\alpha</math>-value	<math>\alpha</math>-value available if previous test positive	<math>\alpha</math>-value available if previous test(s) negative
TCPR: Test NPX vs PLACEBO	0.049	Not Applicable	Not Applicable
TCPR: Test NPX vs [REDACTED]	None	0.049	None
TCPR: Test NPX vs [REDACTED]	None	0.049	None
Percentage of subjects with confirmed perceptible pain relief from 45 minutes to successively earlier minutes in one-minute increments: Test NPX vs Placebo	0.001	0.05	0.001

The four tests in the above family will be conducted as follows: The survival functions for TCPR will be compared between Test NPX and PBO. If it is non-significant at the 0.049 level, then the first test and the following two tests will be failed and the last test (the percentage of subjects with CPR) will be tested at the 0.001 level. If the first test is significant at the 0.049 level, then the second test, the comparison of survival functions for TCPR between Test NPX and [REDACTED], will be compared at the 0.049 level and the following tests will follow the same pattern as for the first test. If the first 3 tests are significant at the 0.049 level, the last test, the percentage of subjects with CPR, will be tested at the 0.05 level.

### 5.3 Statistical Methods

#### 5.3.1 Time to Confirmed Perceptible Pain Relief (TCPR) [REDACTED]

[REDACTED] Time to confirmed perceptible pain relief is defined as the time (in minutes) to perceptible pain relief as indicated on the first stopwatch, provided that the subject also stopped the second stopwatch indicating meaningful pain relief. [REDACTED]

[REDACTED] subjects who do not have relief by 12 hours, who take any type of rescue medication before having relief, or who discontinue before having relief will have time to relief set to 12 hours and be censored at 12 hours. Subjects who take rescue medication after confirmed perceptible pain relief will not be censored. Subjects who received lidocaine 2% after dosing will be treated as subjects taking rescue medication.

██████ TCPR ██████ will be analysed using survival data analysis. The survival function (cumulative proportions of subjects with pain relief at each time point) and the median survival time will be estimated by the Kaplan-Meier method for each treatment. The survival functions will be compared using the Wilcoxon test.

The estimation of the survival functions and the comparison of the survival functions between treatments will be performed by the following SAS codes

```
proc lifetest data=DATASET method=KM outsurv=predict;  
  strata trt;  
  time TIME*censor(x);  
  ods output Quartiles=output1(where=(percent=50));  
run;
```

Sensitivity analyses will be conducted for TCPR to assess the impact of different censoring.

- To assess the impact of censoring at the time of rescue medication for subjects not having meaningful relief, the following approach will be used: For subjects taking rescue medication before having confirmed perceptible pain relief, TCPR will be censored at the time of rescue medication. For those subjects who discontinue before having confirmed perceptible pain relief, TCPR will be censored at the time of discontinuation, approximated using the last observed timepoint ██████. For subjects having perceptible relief but not meaningful relief, TCPR will be censored at 12 hours.
- To assess the impact of censoring at the time of perceptible relief for subjects not having meaningful relief, the following approach will be used: For subjects having perceptible relief but not meaningful relief, TCPR will be censored at the time of perceptible relief. For subjects not experiencing TCPR who discontinue before 12 hours, TCPR will be censored at the time of discontinuation, ██████. For subjects not experiencing TCPR who receiving rescue medication, TCPR will be censored at 12 hours.

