### **14.1. Sample Size Determination**

A sample size of 150 per group for the active treatment arms was chosen based on pharmacokinetic/pharmacodynamics modeling and simulation using data from previous studies[3]. Based on the modeling, it was determined that 150 subjects per active treatment arm would be needed to provide 90% power to reject the null hypothesis of equal distributions for time to confirmed perceptible relief, when comparing Test NPX tablets with [REDACTED] tablets, using a two-sided test at the 0.05 significance level. A sample size of at least 50 subjects per treatment arm provides greater than 90% power to reject the null hypothesis of equal distributions for time to confirmed perceptible relief when comparing Test NPX tablet and placebo assuming median times to relief of 17 minutes for Test NPX and at least 2 hours for placebo.

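### The code printed for the primary analysis in SAP 5.3.1, run on all four arms, gives one 3-df test and no p-value for any of the three pairwise TCPR tests required at 0.049

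*SAP*

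**What the plan says.** **Hypotheses and decision rule.** SAP 5.1 sets up a two-sample null in which S1 and S2 "are the survival functions of each compared treatment, respectively". It lists Test NPX against each commercial product and each naproxen product against placebo. SAP 5.2 orders the tests: "Testing will commence with an assigned alpha = 0.049 and an alpha value of 0.001 will be reserved" for the secondary endpoint. Below Table 2 the first step is spelled out: "The survival functions for TCPR will be compared between Test NPX and PBO". Two further two-arm steps, against the commercial products, follow the same pattern at 0.049. Protocol 14.5 and its Table 5 agree.

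**Analysis set.** SAP 3.1 bases the efficacy analyses on all randomized subjects. SAP 1.2 gives four arms in a 3:3:3:1 ratio, about 150/150/150/50 of 500.

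**Method and code.** SAP 5.3.1 names the Wilcoxon test and continues: "The estimation of the survival functions and the comparison of the survival functions between treatments will be performed by the following SAS codes". One PROC LIFETEST call follows, on a dataset called DATASET, with `strata trt;`. It has no WHERE or BY statement and no pairwise option. Its ODS statement keeps only the 50% quartile, and OUTSURV keeps the curve estimates.

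**Contrast within the SAP.** SAP 5.3.2 labels its GENMOD code for the secondary endpoint as a sample and requests treatment differences explicitly. SAP 5.3.1 does neither.

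**The concern.** The printed code does not carry out the tests that the decision rule needs. A call stratified on a four-level treatment variable tests whether all four curves are equal. Table 2 needs three separate two-arm p-values. A significant four-arm result says only that some arm differs from some other. It does not show that Test NPX differs from placebo, and still less that it differs from either commercial product.

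This is the primary endpoint, and the sequence carries forward. The TCPR steps decide whether testing continues and whether the secondary comparison is made at 0.05 or at 0.001. The text that says how those p-values are produced should therefore produce them.

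**Working it through.** **1. The plan's own figures.** The alpha split is exact: 0.049 + 0.001 = 0.05.

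Protocol 14.1 says: "A sample size of at least 50 subjects per treatment arm provides greater than 90% power" for Test NPX versus placebo, "assuming median times to relief of 17 minutes for Test NPX and at least 2 hours for placebo". With exponential times the hazard ratio is 17/120 = 0.142, and |log HR| = 1.954.
- Events by 12 hours (720 min) with 50 per arm: 50 × 1.000 + 50 × (1 − 2^(−720/120)) = 50 + 49.2 = 99.2.
- Schoenfeld: z = 1.954 × √(99.2 × 0.25) − 1.960 = 9.73 − 1.96 = 7.77, so power exceeds 0.9999.
- With assumed event shares of only 60% and 20% (40 events): 1.954 × √10 − 1.960 = 4.22, and power still exceeds 0.9999.

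The claim of more than 90% is reproduced.

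For Test NPX versus the commercial tablets, the protocol says: "150 subjects per active treatment arm would be needed to provide 90% power to reject the null hypothesis of equal distributions", "using a two-sided test at the 0.05 significance level". It gives no effect size, so the 90% cannot be reproduced. Under assumed proportional hazards with everyone relieved (300 events), 90% needs HR = exp[(1.960 + 1.282)/√(300 × 0.25)] = 1.45; with 70% relieved it needs 1.56. Both power statements are two-arm statements, which fits 5.1 and 5.2 and not a four-arm test.

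**2. Degrees of freedom.** For k arms the Gehan-Wilcoxon statistic uses U_j = Σ Y(t)[d_j(t) − Y_j(t)d(t)/Y(t)] over event times, where Y counts subjects at risk and d counts events. U′V⁻¹U is referred to chi-square on k − 1 df. All randomized subjects: 4 − 1 = 3. A two-arm subset: 2 − 1 = 1. SAP 5.1 and 5.2 need the 1-df test three times.

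**3. How far apart the two answers are.** Simulation: 150/150/150/50 subjects, exponential times, censoring at 720 min, 2,000 trials per scenario, every test at 0.049. The standard error at the nominal level is √(0.049 × 0.951/2000) = 0.5 points. The 17 and 120 minute medians are from Protocol 14.1. The other medians and all non-responder shares are assumptions. Where there are non-responders, the medians apply to those who get relief.

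| Scenario (three active arms identical) | 3-df four-arm test | Two-arm, Test vs commercial 1 / 2 | 3-df positive, neither commercial test positive |
|---|---|---|---|
| Actives 17, placebo 120, all relieved | 100% | 5.8% / 5.3% | 90.0% |
| Same medians; never relieved 15% active, 60% placebo | 100% | 4.8% / 4.9% | 91.3% |
| Weak contrast: 40 vs 60; never relieved 15%, 40% | 93.7% | 5.4% / 4.9% | 84.2% |
| All four arms identical, median 17 | 4.9% | 4.2% / 4.9% | 2.2% |

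The last row shows that both tests hold their level when no arm differs. The first three show that the 3-df result follows placebo. In the second row the overall Test NPX median is about 21.8 min (solve 0.85 × (1 − 2^(−t/17)) = 0.5), not 17. The first row keeps 17 and gives the same picture.

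**The case against.** The strongest reply is that the pairwise tests are already fully specified. SAP 5.1 lists the comparisons, 5.2 gives order and level, and 5.3.1 names the Wilcoxon test. One p-value cannot fill three rows of Table 2, so a statistician who follows 5.2 would not use it. The code is also a template: DATASET, TIME and censor(x) are placeholders. The same call on a two-arm subset gives exactly the 1-df test required. SAP 3.1 says who is analysed, not what is fed to each call.

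Most of this stands, and it limits the point to a mismatch between code and text. What remains is that nothing in 5.3.1 says DATASET is a two-arm subset, the code is presented as what performs the comparison, and it saves no test result under either reading. Parts of 5.3.1 are blacked out, but the sentence introducing the code and the code itself appear complete.

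Two stronger readings are tempting. A reader might infer that the trial will judge superiority over the commercial products by the four-arm p-value, with a false-positive rate near 100%. The documents do not say so: no passage compares an omnibus p-value with 0.049, and 5.2 describes two-arm comparisons. A reader might also infer that pairwise results would be distorted by contrasts drawn from the pooled four-arm data. The plan specifies no such contrast for TCPR, so there is nothing in it to fault on that ground.

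**Conclusion.** The point holds as a minor one. As printed and applied to all randomized subjects, the LIFETEST code in SAP 5.3.1 does not produce the p-value for any of the three pairwise TCPR tests, including Test NPX versus placebo.

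The gap between the printed test and the intended one is large: about 100% against about 5% with identical actives, and 93.7% against about 5% under a deliberately weak placebo contrast. Those rates rest on exponential times and assumed response shares. They measure how different the two tests are and are not an error rate of the trial. Hypotheses, named test, order, alpha, analysis set and sample size are unaffected.

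**What to change.** In SAP 5.3.1:
- State that each TCPR gatekeeping step uses the Wilcoxon test on a dataset restricted to the two arms compared, for example `WHERE trt IN (Test, comparator); STRATA trt / TEST=WILCOXON`, run once per step.
- Save the homogeneity-test output from each call, and name those three p-values as the ones compared with 0.049.
- Keep the four-arm call for the Kaplan-Meier curves and medians only.
- Use the same two-arm form for the comparisons of the commercial products with placebo, which SAP 5.1 lists but Table 2 leaves outside the sequence.

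The cost is a few sentences and a few lines of code, with no added subjects and no protocol amendment. Protocol 14 requires the SAP to be final before database lock and release of the randomization codes, so the change should be made by then.

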### 5.3.2 Earliest Statistically Significant Separation of Test NPX and Placebo on Percentage of Subjects with Confirmed Perceptible Relief

The earliest time of separation between Test ██████ and PBO will be established by comparing the percentage of subjects with confirmed perceptible pain relief starting from 45 minutes to successive earlier minutes in one-minute increments, until statistical significance is no longer achieved. At each one-minute increment, each subject will be categorized as either having experienced confirmed perceptible pain relief by that time or not. The resulting binary response at each time point will be analyzed using logistic regression analysis.

The following is sample SAS code for the logistic regression analyses:

```
proc GENMOD data=DATASET ;  
  
  class trt;
```

```
model responder = trt / dist=BIN link=LOGIT;  
lsmeans trt / diff cl exp;  
run;
```

5.3.3

[REDACTED]

[REDACTED]

[REDACTED]

5.3.5

[REDACTED]

[REDACTED]

[REDACTED]

5.3.6 [REDACTED]

5.3.7 [REDACTED]

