**14.7. Analysis Methods**

**14.7.1. [REDACTED] Time to Confirmed Perceptible Pain Relief**

[REDACTED] time to confirmed perceptible pain relief (TCPR), [REDACTED] will be analyzed using survival data analysis. The survival function (cumulative proportions of subjects with pain relief at each time point) and the median survival time will be estimated by the Kaplan-Meier method for each treatment. The survival functions will be compared using the Wilcoxon test.

Sensitivity analyses will be conducted for TCPR assessing the impact of censoring at the time of rescue medication for subjects not having meaningful relief, and also the impact of censoring at the time of perceptible relief for subjects not having meaningful relief. Further details regarding these analyses will be provided in the statistical analysis plan.

**14.7.2. Earliest Statistically Significant Separation of Test NPX and Placebo on Percentage of Subjects with Confirmed Perceptible Relief**

The earliest time of separation between Test NPX and placebo will be established by comparing the percentage of subjects with confirmed perceptible pain relief starting from 45 minutes to successively earlier minutes in one-minute increments, until statistical significance is no longer achieved. The dichotomized response will be analyzed using logistic regression analysis.

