### 1.2 Study Design

This is a single-dose, randomized, double-blind, placebo- and active- controlled, parallel-group study to evaluate the analgesic onset, efficacy, and safety profile of 440 mg of naproxen sodium administered as two Test NPX 220 mg tablets compared with two commercial products and placebo over a 12-hour period after third-molar extractions. Subjects will undergo dental extraction of three or four third molars. Maxillary third molars may be removed regardless of impaction level. The mandibular extractions must meet one of the following scenarios and must not result in a trauma rating of severe in a mild, moderate, or severe scale:

- two full bony impactions
- two partial bony impactions

- one full bony impaction in combination with one partial bony impaction

Pain assessments will be based on subject self-report. Subjects who meet the randomization criteria (post-surgical pain of moderate to severe on the four-point categorical pain scale [0-no pain, 1-mild pain, 2-moderate pain, 3-severe pain], and at least a score of 5 on the 11-point [0-10] pain intensity numerical rating scale [PI-NRS] at baseline within 4.5 hours of last stitch from dental extractions) will be assigned to one of four treatment groups. This PI-NRS will be within 5 minutes prior to study medication dosing and will be considered the time 0 pain intensity assessment.

Approximately 500 subjects will receive a single 440 mg dose of either Test NPX, [REDACTED] tablets, [REDACTED] capsules, or placebo in a 3:3:3:1 allocation ratio and will be stratified according to gender and baseline pain rating (moderate or severe). To maintain the double-blind nature of the study, an independent third party will administer study drug to blindfolded subjects. No less than approximately 30% of randomized subjects will be either male or female. In addition, no more than approximately 30% of subjects will be 17 years of age at the time of screening.

Self-reported pain intensity will be collected at baseline (time 0). [REDACTED]

[REDACTED] Perceptible pain relief and meaningful pain relief will be collected using two separate stopwatches. Subjects who do not experience any pain relief after dosing will be encouraged, but not required, to wait at least 1.5 hour before using rescue therapy. [REDACTED]

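### SAP 5.3.2 names no test for the earliest-separation step-down; its sample code gives a Wald test that cannot succeed with 0/50 placebo responders, so the sequence can stop too soon

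*SAP*

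**What the plan says.** Protocol 14.7.2 sets the procedure: compare the percentage with confirmed perceptible relief "starting from 45 minutes to successively earlier minutes in one-minute increments, until statistical significance is no longer achieved". On method it says "The dichotomized response will be analyzed using logistic regression analysis". SAP 5.3.2 repeats this: "The resulting binary response at each time point will be analyzed using logistic regression analysis". The protocol synopsis carries the same sentence.

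The only computation shown is introduced by "The following is sample SAS code for the logistic regression analyses". It is PROC GENMOD with treatment as the sole term, a binomial distribution and logit link, and the contrast line "lsmeans trt / diff cl exp". That line produces Wald tests on the log-odds scale. The code has no likelihood-ratio, exact or penalised option. No readable text covers empty or sparse cells. A redaction follows the synopsis sentence, but none shows at that point in Protocol 14.7.2 or SAP 5.3.2.

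Allocation is "in a 3:3:3:1 allocation ratio" among about 500 subjects. SAP 5.2 tests this endpoint at 0.05 if all three TCPR comparisons succeed and at 0.001 otherwise.

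**The concern.** The step-down moves toward the earliest minutes, where placebo responders are fewest. That is where the Wald test for a log odds ratio breaks down. With an empty placebo cell the estimate diverges, its standard error grows faster, and the p-value goes to about 1. With one or two placebo responders the standard error is dominated by the reciprocal of that count, so the test loses power. One non-significant minute ends the sequence, so the reported onset can reflect the test rather than the arms ceasing to differ.

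This is the only secondary endpoint in the alpha-controlled family, and its output is a specific onset minute. Because no statistic is named, Wald, likelihood-ratio and score tests all fit the description and give different answers. With exponential curves at the protocol's medians and alpha 0.05, the median onset is 5, 2 and 3 minutes respectively.

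**Working it through.** **Inputs.** About 500 subjects at 3:3:3:1 give 500 × 3/10 = 150 on Test NPX and 500 × 1/10 = 50 on placebo. SAP 4.4 allows no covariates, so each minute is a 2×2 table. Under SAP 5.3.1, subjects who take rescue or discontinue before relief are censored at 12 hours, so they count as non-responders at every minute up to 45. Protocol 14.1 gives the power statement for placebo "assuming median times to relief of 17 minutes for Test NPX and at least 2 hours for placebo". Two-sided testing is stated for the sample size and assumed here.

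**The plan's own figure.** Protocol 14.1 claims more than 90% power against placebo with at least 50 per arm. With exponential times, the hazard ratio is 17/120 = 0.142, so |ln HR| = 1.954. Over 12 hours, events are about 50 + 50 × (1 − 2^(−720/120)) = 99.2. Then z = 1.954 × √(99.2/4) = 9.73, far above 1.96, so power is about 100%. The claim is reproduced. It concerns TCPR, not the minute-by-minute tests.

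**Wald formula.** With a of 150 and b of 50 responding, z = ln[a(50 − b) / ((150 − a)b)] / √(1/a + 1/(150 − a) + 1/b + 1/(50 − b)).

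- 20/150 vs 1/50: ln(20 × 49/130) = 2.020; SE = √(0.050 + 0.008 + 1 + 0.020) = 1.038; z = 1.95, p = 0.052. Fisher gives p = 0.030.
- 27/150 vs 0/50: 1/b is infinite. An iterative fit returned estimate 23.0, SE 18528, p = 0.999. Fisher gives p = 0.0005.

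**Smallest significant Test NPX count out of 150**

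| Placebo responders of 50 | Wald, 0.05 | Fisher, 0.05 | Wald, 0.001 | Fisher, 0.001 |
|---|---|---|---|---|
| 0 | none | 12 | none | 24 |
| 1 | 21 | 17 | 56 | 31 |
| 2 | 24 | 22 | 49 | 37 |
| 3 | 28 | 27 | 50 | 42 |
| 4 | 31 | 32 | 52 | 47 |

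At alpha 0.05 the two tests agree from 5 to 7 placebo responders. At 0.001 Wald stays weaker there: 55 vs 50, 59 vs 55, 62 vs 59. At 0.001 Wald also needs more Test NPX responders when placebo has 1 (56) than when it has 2 (49), which is the wrong direction.

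**How often placebo is empty.** For exponential placebo times with median M, P(0/50 by minute t) = 2^(−50t/M). At 3, 5 and 10 minutes this is 0.42, 0.24 and 0.06 for M = 120, and 0.65, 0.49 and 0.24 for M = 240.

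**Effect on the reported minute.** The backward step-down was simulated in 20,000 trials per curve pair (Monte Carlo SE of the mean delay at most 0.05 min). Delay is Wald minus Fisher. All shapes are assumptions; only the medians 17 and at least 120 come from the protocol.

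| Assumed curves | Mean delay, 0.05 (min) | Median onset, Wald vs Fisher, 0.05 | Wald later, 0.05 | Mean delay, 0.001 (min) |
|---|---|---|---|---|
| 85% of Test NPX ever respond; 40% of placebo on the same early curve | 0.1 | 12 vs 12 | 15% | 0.4 |
| Lognormal Test NPX (sigma 0.6); 40% early placebo response | 0.3 | 11 vs 11 | 23% | 0.7 |
| Same Test NPX curve; exponential placebo, median 120 | 0.7 | 10 vs 10 | 32% | 1.6 |
| 45% of placebo responding, median 22 min | 1.1 | 10 vs 9 | 53% | 1.5 |
| Exponential, medians 17 and 120 | 2.2 | 5 vs 3 | 69% | 3.6 |
| Exponential, medians 17 and 240 | 5.4 | 6 vs 3 | 86% | 6.5 |

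A slower-starting set of curves gives larger gaps. With Weibull shape 2, a 5-minute lag, 20% Test NPX non-responders, and placebo response of 20%, 10% or 5% by 45 minutes, median onset at alpha 0.05 was 16, 20 or 26 minutes by Wald against 9 by Fisher.

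**Mechanism, exponential 17 vs 120.** At alpha 0.05, 39% of trials stop at a zero-placebo minute where Fisher is significant, and these supply 1.8 of the 2.2 minutes. At 0.001 such trials are 5% and supply 0.5 of the 3.6 minutes; sparse non-zero counts supply the rest.

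**The case against.** The Wald test is valid here. Its maximum exact size over the 150 vs 50 tables is 0.0485 at alpha 0.05 and 0.0007 at 0.001. Where the assumed curves differ at every positive time there is no true separation minute, so a late onset is late only relative to another test. The size depends on the curves: at alpha 0.05 the median onsets agree in three of the six pairs and differ by one minute in a fourth. The 2- to 3-minute gaps need exponential Test NPX times, which put 11.5% of Test NPX subjects at relief by minute 3. Fisher is one choice among several, and the code is only a sample.

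Much of this stands. There is no validity problem, and the delay cannot be fixed from the documents. But a test that cannot reject at 0/50 for any Test NPX count, and that asks for more evidence at 1/50 than at 2/50 (alpha 0.001), is defective in these tables; this goes beyond a preference between sound tests. The sample label does not help, because nothing else names the test. The alternatives are less secure on size: maximum exact size at alpha 0.05 is 0.078 for the likelihood-ratio test, 0.053 for the score test (0.0021 at 0.001) and 0.0507 for the Firth version, a trivial excess in that last case.

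**Conclusion.** The concern holds and should be fixed. The failure at 0/50 is certain and depends on neither alpha nor the Test NPX rate. The weakness at low non-zero counts lies mainly at 1 to 2 placebo responders for alpha 0.05 and extends to at least 7 for alpha 0.001. The delay rests on assumed curves: negligible if placebo responds early and often, several minutes or more if placebo response is slow.

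The consequence is limited. The error runs against Test NPX, does not inflate type I error, and leaves the TCPR tests alone. The 0.001 level, where the loss is larger, applies if any TCPR comparison fails. The stated 90% power for the tablet comparison, taken at face value, implies about a 10% chance of that from this comparison alone (100% − 90%). The readable text gives no power for the capsule comparison.

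**What to change.** In SAP 5.3.2 and Protocol 14.7.2, with a conforming edit to the matching synopsis sentence, name the two-sided Fisher's exact test as the decision p-value at every minute, unstratified to match SAP 4.4. Keep the logistic odds ratio as a descriptive estimate. Leave the step-down order and the alpha allocation as they are.

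Do not confine Fisher to minutes with an empty cell. In the exponential 17 vs 120 case, that hybrid still leaves 0.4 of the 2.2 minutes' mean delay at alpha 0.05 and 3.2 of the 3.6 at 0.001.

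The cost is a few lines in the SAP and the matching protocol sentences before database lock, with no new data. Fisher is slightly conservative (maximum exact size 0.045 at alpha 0.05 and 0.0008 at 0.001). At alpha 0.05 it needs one more Test NPX responder than Wald at 4/50 (32 vs 31), and it gave a later onset than Wald in 0.2% to 6% of simulated trials.
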